4 STUDY POPULATIONS

Study populations intended for analysis will be defined as follows: Intent-to-Treat (ITT), Per-Protocol (PP), and Safety. The ITT population will represent the primary analysis population to evaluate the treatment groups on all efficacy endpoints. The primary efficacy endpoint will also be analyzed for the PP population, which is the secondary analysis population.

4.1 Intent-to-Treat Population

The ITT population will include all randomized patients who received at least one dose of study drug and have a baseline and at least one post-baseline efficacy assessment. There can be a different number of patients (N) in the ITT population for each of the four efficacy measures (LIC, serum ferritin, cardiac T2*, and quality of life) if some of the patients don't have post-baseline data on all of the three efficacy measures. All efficacy analyses will be based on the ITT population.

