## PROTOCOL SYNOPSIS

**Title of the Study:** The efficacy and safety of Ferriprox® for the treatment of transfusional iron overload in patients with sickle cell disease or other anemias.

**Protocol Code:** LA38-0411

**Development Phase:** Phase IV

**Sponsor:** ApoPharma Inc.

**Principal Investigator:** [name]  
The Children's Hospital of Philadelphia  
Philadelphia, PA, USA

**Study Center:** Multicenter

**Planned Study Period:** Individual patient treatment duration of 52 weeks. At the end of the 52 weeks of treatment, patients will be invited to participate in a 2-year extension phase.

**Study Objectives:** Primary:

To determine the efficacy of deferiprone vs. deferoxamine in the treatment of iron overload in patients with sickle cell disease or other anemias.

Secondary:

- To evaluate the effect of deferiprone vs. deferoxamine on the patients' quality of life;
- To evaluate the safety and tolerability of deferiprone vs. deferoxamine.

**Study Design:** This study is a 52-week, prospective, multi-center, two-arm, randomized, open-label, parallel design study of deferiprone vs. deferoxamine.

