### **3.3 Study Sites and Study Duration**

Study sites will be located in but not limited to countries in North America, Europe, and the Middle East. While the goal will be to keep the number of sites to a minimum, it is expected that the study will engage sites worldwide due to the anticipated difficulty in enrolling patients with a 33% probability of being allocated to the deferoxamine treatment arm.

Each patient is expected to participate in the study for approximately 60 weeks (from the Screening Visit to the End of Study Visit).

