7.5 Sensitivity Analysis

Sensitivity analyses will be performed on the primary efficacy measure, LIC. As a sensitivity analysis, the missing data imputation will be repeated with the LOCF method being used for all drop-out patients in the deferoxamine group and the “worst value” method being used for all drop-out patients in the Ferriprox group. This imputation approach will result in the worst case scenario for the Ferrirox group. In addition, the primary efficacy analysis will be repeated on a dataset involving only patients who have at least 6-month LIC data in the ITT population to assess the impact of early patient withdrawal on the results of the ITT analysis.

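### The worst-case analysis in SAP 7.5 gives no imputed value to randomised patients who were never dosed or have no post-baseline LIC, and no all-randomised analysis is planned

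*SAP*

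**What the plan says.** **Analysis set.** SAP 4.1, like Protocol 11.2.5.1, defines the ITT set as randomised patients who "received at least one dose of study drug and have a baseline and at least one post-baseline efficacy assessment". Membership depends on the measure: "There can be a different number of patients (N) in the ITT population for each of the four efficacy measures". The section ends: "All efficacy analyses will be based on the ITT population". For LIC, then, a patient needs a dose, a baseline LIC and a later LIC.

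**Sensitivity analyses.** SAP 7.5 plans two for LIC. In the first, all deferoxamine drop-outs get LOCF, with the worst-value "method being used for all drop-out patients in the Ferriprox group". The SAP adds: "This imputation approach will result in the worst case scenario for the Ferrirox group". The second is the primary analysis "repeated on a dataset involving only patients who have at least 6-month LIC data in the ITT population", which is narrower than the ITT set. Neither names a wider set.

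**When a post-baseline LIC arises.** The protocol schedules liver MRI at Weeks 26 and 52, or at the Early Termination visit if that comes first (Synopsis, 3.2, 5.9). A footnote to the schedule of events says a withdrawing patient must be seen for that visit. Protocol 4.5 asks for a return visit only where it is possible.

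**Design.** The trial is a "two-arm, randomized, open-label, parallel design study of deferiprone vs. deferoxamine".

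**The concern.** Both conditions for entering the set are met or failed after randomisation, with the assigned drug known to patient and investigator. Losses at that stage can depend on the arm. The protocol shows routes in each:

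- Deferoxamine: dosing must be deferred for some patients whose baseline ferritin result is not yet available, while deferiprone titration can start (Protocol 7.4).
- Deferiprone: agranulocytosis is said to peak at 5 months (Protocol 1.2) and requires withdrawal (4.5). That is before the first scheduled post-baseline LIC at Week 26.

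The first analysis in 7.5 is the plan's stress test for missing LIC data. If the patients with no follow-up LIC at all lie outside it, it can show robustness only for drop-outs who left some LIC data behind. The SAP's sample-size section says a non-inferiority conclusion at the interim may lead to early termination of the study, so a reader may lean on this analysis.

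**Working it through.** **1. Who is left out.** Reading SAP 4.1 and 7.5 together for LIC:

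| Randomised patient | In the ITT set for LIC? | Imputed value in 7.5? |
|---|---|---|
| Dosed, leaves early, has Early Termination MRI | Yes | Yes |
| Dosed, leaves after a Week 26 MRI | Yes | Yes |
| Dosed, leaves with no post-baseline LIC | No | No |
| Never dosed | No | No |

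For the last two rows LOCF has no post-baseline value to carry, and 7.5 gives no other rule.

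**2. The plan's own figures.** Inputs: margin 2 mg/g dw, SD 4 in both arms, true difference 0 (Protocol 11.2.4 and 18.4); 142 and 71 patients and two-sided alpha 0.0399 (SAP sample-size section and 3.7).

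- Protocol 18.4, groups of 79 and 158, one-sided 0.025: noncentral-t power 95.1%, against 95.017% stated. It reproduces.
- SAP 3.7: 0.05 × ln(1 + 1.718 × 0.71) = 0.0399. It reproduces.
- SAP interim power, 142 and 71: 91.4% by noncentral t, against 89% stated. It does not reproduce at the stated alpha. That is a separate matter, and nothing below uses the 89%.

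**3. Room for an observed difference.** SE = 4 × √(1/142 + 1/71) = 0.581. The 96.01% half-width is 2.068 × 0.581 = 1.20. Non-inferiority needs an observed difference of at most 2 − 1.20 = 0.80 mg/g dw. This uses an unadjusted t interval, not the SAP's mixed model.

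**4. Simple illustration.** Assumed: 4 to 7 of 142 deferiprone patients (2.8% to 4.9%) have no post-baseline LIC and are restored at 8 mg/g dw (2 SD) above the mean change.

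- Deferiprone alone: 4 × 8/142 = 0.23; 7 × 8/142 = 0.39. The result is the same if deferoxamine patients are also lost but restored at their group mean.
- Same share lost on deferoxamine, restored at zero change against an assumed mean of −4: subtract 0.028 × 4 = 0.11 or 0.049 × 4 = 0.20. The net shift is about 0.11 to 0.20.

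**5. With the group's actual worst value.** With 142 normal changes (mean −4, SD 4), the worst is expected near +6.5, a gap of about 10.5. In simulation (3,000 runs per scenario, equal shares lost, all other patients complete):

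| Share lost (deferiprone, deferoxamine) | Shift: deferoxamine at zero / at mean | P(non-inferiority), left out | P(non-inferiority), restored: zero / mean |
|---|---|---|---|
| 2% (3, 1) | 0.17 / 0.22 | about 90% | 82% / 82% |
| 5% (7, 4) | 0.29 / 0.51 | about 89–90% | 76% / 62% |
| 10% (14, 7) | 0.63 / 1.02 | about 89% | 50% / 27% |

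**6. Is 3–5% plausible?** The documents state no drop-out rate. Protocol 1.4 does expect deaths: 7.0 per 100 person-years × 300 = 21 in 52 weeks, if all patients have SCD. Spread evenly, about 10.5 of 300 (3.5%) would fall before Week 26 and could have no Early Termination scan. This is a natural-history rate, possibly high for patients screened for unstable illness, and it says nothing about the split by arm. No figure in the documents supports 10%.

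**The case against.** **The Early Termination MRI closes most of the gap.** It is planned, patients are reminded of the visit throughout, and anyone scanned stays in the set and gets the worst value. This stands. A reader might infer that the earliest drop-outs as a class are omitted, and the documents do not support that. The gap is confined to patients never dosed and those never scanned after baseline.

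**SAP 7.5 does not itself limit the imputation to the ITT set.** Correct: its mention of that set belongs to the second, 6-month analysis. The limit comes from the closing sentence of SAP 4.1. Reading the drop-outs in 7.5 more widely would contradict 4.1 and still leave deferoxamine patients with no post-baseline LIC without a rule.

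**Protocol 3.3 does not show losses that flatter deferiprone.** It speaks of "anticipated difficulty in enrolling patients with a 33% probability of being allocated to the deferoxamine treatment arm", which concerns reluctance before randomisation. A reader might take it as evidence of unequal loss afterwards, but it does not say so. If the reluctance carried over, it would remove deferoxamine patients rather than deferiprone patients.

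**The size is assumed.** This stands, and equal loss with zero change on deferoxamine halves the simple figure.

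**The loss will be visible.** Tables 14.1.1, 14.1.2 and 14.1.4 give randomised, exposed and ITT counts and reasons for non-completion by arm. They show how many patients are lost, not what including them does to the result.

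**The definition is open and identical in both documents.** True, so renaming the set would only be labelling. The problem is that the worst-case description claims more than the set allows.

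**Conclusion.** The point holds in a limited form. As written, the first analysis in SAP 7.5 is not the worst case for deferiprone, because randomised patients with no dose or no post-baseline LIC get no value in it, and no other planned analysis covers them.

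Size and direction are unknown. On the assumed 3–5% loss, the omitted shift is 0.23 to 0.39 mg/g dw with loss on deferiprone only, and about 0.11 to 0.20 with equal loss and zero change on deferoxamine. The observed difference may be at most about 0.80. Using the expected worst value at 5% loss in both arms gives 0.29 to 0.51. None of these shifts alone uses up the 0.80, but they come on top of the shift from drop-outs already imputed and any difference observed. These figures rest on SD 4, normal changes with mean −4, no true difference, and the worst value taken as a change from baseline.

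A reader might go further and infer that the primary non-inferiority result is biased towards deferiprone. The primary analysis uses the same set and has the same gap, but nothing in the documents fixes the direction, and the non-inferiority criterion does not depend on 7.5. This is a cheap improvement to the sensitivity analysis, not a defect that overturns the plan.

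**What to change.** In SAP 7.5, keep the planned analysis and add one run of the worst-case imputation on **all randomised patients with a baseline LIC**. Baseline LIC is an entry criterion, so nearly every randomised patient should have one. State these rules:

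- Deferiprone patients without a post-baseline LIC get the worst value in their group. Some of them never took the drug, which is acceptable in a stress test that follows the assigned arm.
- Deferoxamine patients without one get the deferoxamine group mean change (the worst case for deferiprone). A second version gives them zero change, that is, baseline carried forward.
- Where on-study transfusional iron input is missing, use the 3-month pre-baseline input, which SAP 9.3 calculates in the same mg/kg/day units, as the covariate. Without this rule the model in SAP 7.1 would drop the restored patients again.
- Say whether the rules fill Week 26 as well as Week 52.

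If the run is not added, remove the worst-case wording from 7.5. Renaming the set alone would not answer the point.

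Cost: one extra run in two versions, a few lines of specification, and a possibly less favourable sensitivity result. No new data collection is needed.

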4.2 Per-Protocol Population

The Per-Protocol (PP) population will include all enrolled patients who will have completed the study, have no major protocol violations, and have an efficacy measure by the end of the study. Prior to database lock, major protocol violations will be determined and the affected patients will be excluded from the PP population. Major protocol violations will include (but not be limited to) the following:

- Patients who did not fulfill the LIC > 7 mg/g inclusion criterion.
- Patients who were not compliant with the treatment (< 80% compliance).
- Patients who took iron chelator medications other than the assigned study medication during the course of the study.

Only the primary efficacy measure, which is LIC, will be performed with the PP population.

4.3 Safety Population

The Safety population will include all enrolled patients who took at least one dose of study drug.

5. HANDLING OF MISSING DATA

In the efficacy analyses, for patients who were terminated from the study prior to Month 12, if their last efficacy measures were obtained within 30 days of Month 12, the data obtained will be treated as the Month 12 data. For early termination that occurred outside this window, the last observation carried forward (LOCF) method will be used to fill the missing data when the early termination was not caused by worsening of disease conditions or inadequate efficacy of the drug. For early termination due to worsening

of disease conditions or inadequate efficacy of the drug, as judged by assessing the AE log, the “worst value” method will be used. That is, the worst value of all patients from the corresponding treatment group will be used to impute the missing data at that time point. For missing data due to missed visit, the LOCF method will be used to fill the void.

For safety data analysis, no imputation will be performed on the missing data, and analysis will be based on observed cases (OC).

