## 4.5 Withdrawal Criteria

A patient has the right to withdraw from the study at any time and for any reason without consequence to future care by the Investigator or study center. The reason for withdrawal will be sought.

When a patient decides to withdraw from the study, he/she should always be contacted, not only to determine the reason(s) for withdrawing, but also to determine if there were any adverse events (AEs). Whenever possible, the patient should return for a clinic visit at the time of or soon after discontinuation of study medication but no later than 1 month after treatment discontinuation. All investigational products and materials should be returned. If any AEs occurred, the Investigator must attempt to follow up with the outcome for 30 days post-study withdrawal.

Data collected for patients who are withdrawn after receiving the study drug should be evaluated for efficacy and safety.

If, for any reason, the Investigator decides to withdraw a patient before completing the study, the reason for withdrawal must be entered into the source document and the electronic case report form (eCRF).

A patient may be withdrawn from the study at any time for any of the following reasons:

- Patient request;
- Medical reasons considered significant by the patient and/or Investigator;
- Requirement for concomitant medication that may interfere with the evaluation of study medication, or may be contraindicated;
- Occurrence of other illnesses that affect the patient's further participation in the study or evaluation of study medication;
- Significant changes in QTcF interval (defined as QTcF change of greater than 60 ms) are detected;
- Any other situation where, in the opinion of the Investigator, continuation of the study would not be in the best interest of the patient.

A patient **must** be withdrawn from the study if any of the following conditions apply:

- Pregnant or planning to become pregnant (see [Section 9.2](#) Procedures in Case of Pregnancy);
- Occurrence of any adverse reaction characterized as life-threatening or disabling;

- Non-compliance with blood counts. During the first 6 months, if a patient misses a weekly ANC monitoring visit, then missing a further 3 of the next 5 visits (i.e., a total of 4 out of 6) will result in automatic withdrawal. During the last 6 months, ANC monitoring will be done biweekly, and missing 3 consecutive biweekly blood counts will result in automatic withdrawal.

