### **6.4 Rescue Medication**

Rescue medication (intravenous administration of deferoxamine or combination of 2 iron chelators: deferiprone, deferoxamine or deferasirox) for the treatment of iron overload will not be allowed during the study. Should symptoms become intolerable for the patient, dose adjustment should be attempted. If the treatment is unsuccessful, the Investigator may decide to withdraw the patient from the study to optimize treatment.

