#### **8.2.4.1 Definition of Medical/Adverse Events**

**Medical Event:** Any new untoward medical occurrence or worsening of a pre-existing condition in a patient that occurs after signing the ICF but before receiving an investigational product.

**Adverse Event:** An AE is any untoward medical occurrence in a clinical investigation in a patient administered a pharmaceutical or other therapeutic product, not necessarily

having a causal relationship with this treatment. An AE can therefore be any unfavourable and unintended sign, symptom or disease temporally associated with the use of a product, whether or not considered related to that product.

An AE does include:

- exacerbation of a pre-existing illness. This includes acute episodes/crisis of a chronic underlying condition.
- an increase in frequency or intensity of a pre-existing episodic event or condition
- a condition detected or diagnosed after study treatment administration, even though it may have been present prior to the start of the study
- a continuous persistent disease or symptom present at baseline that worsens following the start of the study

An AE does not include:

- a pre-existing disease or condition present or detected at the start of the study that does not worsen
- surgical procedures that had been planned prior to enrolment into the study
- the disease or disorder being studied, or a sign or symptom associated with the disease or disorder, unless it has worsened
- an overdose of either the study treatment or concurrent medication without any signs of symptoms

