### 11.4 Definition of Analysis

For patients who were terminated from the study prior to Month 12, if their last efficacy measures were obtained within 30 days of Month 12, the data obtained will be treated as the Month 12 data. For early termination that occurred outside this window, the last observation carried forward (LOCF) method will be used to fill the missing data when the early termination was not caused by worsening of disease conditions or inadequate efficacy of the drug. For early termination due to worsening of disease conditions or inadequate efficacy of the drug, as indicated in the eCRF, the “worst value” method will be used. That is, the worst value of all patients for the corresponding treatment group will be used to impute the missing data at that time point. For missing data due to missed visit, the LOCF method will be used to fill the void.

As a sensitivity analysis, the analysis will be repeated with the LOCF method being used for all drop-out patients in the deferoxamine group. Other sensitivity analyses, where appropriate, will be detailed in the SAP.

For safety data analysis, no imputation will be performed on the missing data, and analysis will be based on observed cases (OC).

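### SAP section 5 chooses between worst-value and LOCF imputation by a judgement on the AE log, against Protocol 11.4, so a withdrawal for inadequate efficacy can receive LOCF in the primary LIC analysis

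*SAP*

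**What the plan says.** Both documents impute missing Week 52 efficacy data after early termination by cause of withdrawal.

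- **LOCF** applies, in the SAP's words, "when the early termination was not caused by worsening of disease conditions or inadequate efficacy of the drug".
- **Worst value** applies to the remaining early terminations: "the worst value of all patients from the corresponding treatment group will be used to impute the missing data at that time point".
- **How the cause is established** is where they part. Protocol 11.4 reads "For early termination due to worsening of disease conditions or inadequate efficacy of the drug, as indicated in the eCRF". SAP section 5 keeps that sentence but puts "as judged by assessing the AE log" in place of the reference to the eCRF. The SAP text gives no reason for the change.

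Protocol 4.5 and 5.10 already require the reason for withdrawal to be recorded in the source document and the eCRF. The SAP's shell for Table 14.1.4 lists six reasons for not completing: adverse event, voluntary withdrawal, lost to follow-up, Investigator decision, protocol violation and other. Each has a detail column, and none is labelled inadequate efficacy.

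SAP 7.5 adds a sensitivity analysis of LIC that ignores the cause of withdrawal: LOCF for every deferoxamine drop-out and worst value for every Ferriprox drop-out.

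**The concern.** The rule is meant to stop a treatment failure from being analysed at the value last seen before the patient left. It works only if failures are recognised, and an AE log is not designed to record why a patient left the study. A patient whose iron load simply does not fall may be withdrawn without any entry there, and the SAP's rule then defaults to LOCF.

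The classification is also a patient-level judgement that feeds the primary non-inferiority estimate in an open-label trial. The SAP does not say who makes it, by what criteria, when, or whether arm and LIC results are hidden. No planned analysis applies the trigger written in Protocol 11.4, so the report would not show what difference the substitution made.

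**Working it through.** **Can an inadequate-efficacy withdrawal be absent from the AE log?**

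1. Protocol 6.4 allows it to happen: "If the treatment is unsuccessful, the Investigator may decide to withdraw the patient from the study to optimize treatment".
2. Protocol 8.2.4.1 lists what is not an AE, including "the disease or disorder being studied, or a sign or symptom associated with the disease or disorder, unless it has worsened". Iron load that has failed to improve, but has not worsened, need not be an AE.
3. The same section counts a baseline disease that worsens as an AE, and 8.2.4.2 requires clinically significant abnormal assessments to be recorded as AEs if they meet the AE definition. A clear rise in LIC can therefore reach the log.
4. Protocol 8.2.4.3 says AEs related to the underlying condition are recorded separately. This leaves it unclear whether the log consulted would hold all disease worsening.

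So non-improvement without worsening can be missed, while worsening may or may not be.

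**What would a missed case do to the estimate?**

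The documents give no stated figure to reproduce, no drop-out count and no worst LIC value. The following is an illustration.

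Inputs:
- 142 Ferriprox and 71 deferoxamine patients at the interim analysis (SAP sample-size text)
- margin 2 mg/g dw and two-sided α 0.0399 (SAP 7.1)
- SD 4 mg/g dw (Protocol Appendix 18.4)
- gap between worst value and LOCF of 5 to 10 mg/g dw (**assumed**)

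Formula, unadjusted, with all patients taken as analysed: shift in the difference = k × gap / n of the arm, where k is the number of patients given LOCF instead of worst value. The difference is Ferriprox minus deferoxamine, and a larger change in LIC is worse.

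| Missed failures | Gap 5 | Gap 10 | Direction |
|---|---|---|---|
| 1 Ferriprox | 5/142 = 0.035 | 10/142 = 0.070 | favours Ferriprox |
| 1 deferoxamine | 5/71 = 0.070 | 10/71 = 0.141 | against Ferriprox |
| 3 Ferriprox | 0.106 | 0.211 | favours Ferriprox |
| 3 deferoxamine | 0.211 | 0.423 | against Ferriprox |

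Three missed Ferriprox failures come to 0.106/2 = 5% to 0.211/2 = 11% of the margin. Three is also an assumed count.

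For scale, SE = 4 × √(1/142 + 1/71) = 0.581. The 96.01% CI half-width is 2.055 × 0.581 = 1.19, so non-inferiority needs a point estimate of at most 2 − 1.19 = 0.81. Three missed Ferriprox failures would use 0.106/0.81 = 13% to 0.211/0.81 = 26% of that allowance.

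The two directions can cancel. With equal gaps, two missed Ferriprox failures (2 × gap/142) exactly offset one missed deferoxamine failure (gap/71). A net bias needs the proportion missed, or the gap, to differ between arms.

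**The case against.** The strongest reply is that this is a wording conflict with limited consequences. Taken in turn:

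- **The AE log is part of the eCRF.** Protocol 8.2.4.3 puts AEs on an eCRF page, and Protocol 11.4 says only that the eCRF decides, without naming the withdrawal reason. The SAP could be read as specifying which page to use. This stands as a point about wording. It does not make the AE page the right source, because a withdrawal without an AE leaves nothing on it.
- **Failures are not missed wholesale.** A reader might infer that all inadequate-efficacy withdrawals are lost. The documents do not support that, since worsening can be logged.
- **The rule does not systematically hide failure in Ferriprox's favour.** A reader might infer this too. A missed deferoxamine failure makes the comparator look better, which is conservative for the non-inferiority claim.
- **Unmasked assessment is an inference.** The SAP names nobody. The eCRF withdrawal reason is itself entered by an Investigator who knows the arm, so it is not free of this problem either. It is, however, recorded when the patient leaves and does not have to be reconstructed afterwards.
- **LOCF is not always favourable.** Protocol 5.9 includes a liver MRI at the early termination visit. If it is done, LOCF carries that measured value, including any rise. This narrows the gap for such patients.
- **SAP 7.5 stress-tests the harmful direction.** If non-inferiority holds with worst value for every Ferriprox drop-out and LOCF for every deferoxamine drop-out, missed Ferriprox failures cannot explain it. This is a substantial protection. But if that analysis fails while the primary succeeds, it cannot show what Protocol 11.4's rule would have given, because it ignores the cause of withdrawal.

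**Conclusion.** The concern holds in a limited form. SAP section 5 conflicts with Protocol 11.4 on what triggers worst-value imputation in the primary analysis, and the source it substitutes can miss a patient withdrawn for inadequate efficacy without worsening. The SAP leaves the assessor, masking and timing of the judgement open.

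The size cannot be determined from the documents. With the assumed 5–10 mg/g dw gap, the effect is about 0.04–0.07 mg/g dw per missed Ferriprox failure and 0.07–0.14 per missed deferoxamine failure, in opposite directions. These are unadjusted figures at 142 and 71 patients. A smaller analysed population would make each patient count for slightly more, and a measured early-termination LIC would usually make the gap smaller. A few cases would move the estimate by tenths of a mg/g dw, which matters only if the result lies near the boundary.

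The documents do not support a claim of deliberate or one-sided bias. The point should be corrected because the primary rule can work against its own purpose and a better source is already collected.

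**What to change.** In SAP section 5:

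1. Make the eCRF withdrawal reason and its free-text detail the primary trigger, with the AE log as supporting evidence only.
2. State how the existing categories, in particular Investigator decision, Voluntary withdrawal and Other, map to worst value or LOCF.
3. Have staff masked to treatment arm and LIC results classify unclear cases, and fix the classification before database lock.
4. Report by arm, in Table 14.1.4, the number classified as inadequate efficacy or worsening.

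A new table row alone is not enough. The 213 interim patients were projected to have finished or withdrawn by November 30, 2018, and a row cannot create a reason code that was not collected. The mapping and the detail field have to do that work.

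The cost is a revised SAP paragraph, one table line and a short masked review of drop-outs. No new data collection is needed.
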